4.2 Study Outcomes

4.2.1 Primary Outcomes

Change in symptom burden from baseline to 12weeks as measured by the Dialysis Symptom Index (DSI) Severity Score (Appendix B-1). This will be measured as the proportion of individuals who have a decline of 7 points or more in symptom burden as defined by DSI symptom severity score from baseline to 12weeks. The DSI is a 30-item self-administered questionnaire with low administrative burden developed to measure the presence (yes/no) and severity ("how much did it bother you" by 5 point Likert-scale ranging from "not at all" to "very much") of common emotional and physical symptoms over the previous week in individuals receiving maintenance HD.⁵¹ Symptom severity scores can range from 0 to 150. A 7-point change in severity score is likely to be clinically significant because this magnitude of change is: a) consistent with the resolution/addition of 1 "very bothersome" symptom plus a 1 point change in severity of 2 symptoms and likely to be significant to patients; and b) is approximately 1 standard error of the mean based on our pilot data (SD 30, n=18) and consistent with distribution-based methods. The DSI has been shown to be reliable in predicting HRQOL in multiple studies in North American and European HD populations.^{6,51}-

Change in symptom burden from baseline to 12weeks as measured by modified DSI Severity Score. Based on our experience and evidence from small clinical trials, we anticipate that the maximum benefit from exercise will occur in a subset of symptoms on the DSI. These include: a) muscle cramps; b) restless legs; c) feeling tired or lack of energy; d) difficulty concentrating; e) worrying; f) feeling nervous; g) trouble falling asleep; h) feeling irritable; i) feeling sad; j) feeling anxious. Thus, we will perform a subgroup analysis of DSI severity scores for the 11 symptoms listed above. This pragmatic approach will lead to less participant burn out than if individual measures were used for each symptom.

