9.2 Sample Size and Power

Based on the limited literature published in this area, we expect an absolute difference of 25% between the intervention and control groups in the proportion of individuals in whom DSI severity score decreases by 7 points or more over time.

We predict DSI score will decrease in 50% of the intervention group and 25% of the control group at 12weeks (baseline prevalence of symptoms assumed to be 50%). A sample size of 58 patients in each arm will allow us to detect this difference with 80% power (alpha 0.05). We conservatively anticipate 30% dropout.⁸³ Therefore, a target sample size of 150 participants (75 participants per study arm) is proposed.

This sample size will allow us to detect a 7-point difference in mean change in DSI severity score using standard deviation of 16 with 80% power and alpha 0.05. This sample size (n=75 in each arm) will also provide 80% power with 0.05 alpha to detect a 12-point difference between groups in mean change in HRQOL measured using EQ-VAS (considered clinically important difference in other chronic diseases)⁸⁵ and a 30% absolute difference in proportion of individuals endorsing deficits in each domain of EQ5D-3L over time assuming 50% baseline deficit and development of new deficits in an additional 10% of the control group and a reduction in deficits in 15% of the intervention group.

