9.3 Description of Statistical Methods

9.3.1 Primary Outcome

Developed in consultation with a statistician ([name], Chronic Disease Innovation

Centre) familiar with RCTs and our study outcomes, analysis will be performed in an intention-to-treat manner on a case available basis. Change in DSI severity score from baseline to 12 weeks will be compared between groups by independent two-tailed t-test or Mann-Whitney U test depending on distribution and using generalized linear mixed models with study timepoint as a random effect and adjusted for baseline DSI score. In a subgroup of individuals whose baseline DSI score is >7, the proportion of individuals whose DSI severity score has improved by 7 or more points from baseline to 12 weeks will be compared between groups at each study time point using Chi-square test.

Multiple logistic regression will be performed to determine predictors of a >7 point change in DSI severity score over time and adjusted for time varying confounders using a marginal structural model. Interaction terms for sex and baseline DSI score will also be inputted into the model. Although study group will be the primary predictor in this model, other key predictors of symptom burden (including baseline DSI score, diabetes status, ischemic heart disease (IHD), age, gender, race, smoking status, serum albumin level, hemoglobin, baseline physical function, physical activity level and interaction terms for gender/intervention and baseline DSI score/intervention) will also be tested in a step-wise manner.

If **missing outcome data** is greater than anticipated (25%) we will impute them according to current FDA/NAS/NRC recommendations using multiple imputation with chained equations ⁸⁶⁻⁸⁸. Specifically, multiple imputation creates 20-40 complete datasets with plausible values from the model-based predictive distributions, and pooled estimates and standard errors are obtained through the use of Rubin's combining rules. These models are predicated on the assumption that the data are missing at random (MAR). Finally, the robustness of the inferences about treatment effects to violations of the MAR assumptions will be evaluated through a sensitivity analysis ⁸⁸.

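### The 80% power claimed for a 7-point difference in mean DSI change is not reproduced from its own inputs (76% at 75 per arm, about 60% after the planned dropout), and its SD of 16 has no source

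*Combined protocol and SAP*

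**What the plan says.** Section 9.2 first sizes the trial on the proportion whose DSI severity score falls by at least 7 points: 58 per arm for 80% power, 30% anticipated dropout, and then "a target sample size of 150 participants (75 participants per study arm) is proposed". It goes on to make a second claim: "This sample size will allow us to detect a 7-point difference in mean change in DSI severity score using standard deviation of 16 with 80%". The percentage is power, and the significance level given with it is 0.05. The next sentence, on the EuroQol measures, makes the sample size explicit: "This sample size (n=75 in each arm) will also provide 80% power with 0.05 alpha". No reference, pilot value or correlation accompanies the 16.

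Section 9.3.1 gives the matching analysis: mean change from baseline to 12 weeks "will be compared between groups by independent two-tailed t-test or Mann-Whitney U test depending on distribution", with a mixed model adjusted for baseline DSI alongside. Analysis is on available cases, with multiple imputation if more than 25% of outcomes are missing.

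The only DSI SD taken from data is in Section 4.2.1, repeated in 4.2.3. There the 7-point threshold is defended because it "is approximately 1 standard error of the mean based on our pilot data (SD 30, n=18"). The text does not say whether 30 is the SD of a score at one visit or of a change.

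**The concern.** There are two gaps. First, the power statement can be checked from its own four inputs (7 points, SD 16, alpha 0.05, 75 per arm), and it falls short. It also takes no account of the dropout stated a few lines above it. Second, the plan uses SD 30 to justify 7 points as the meaningful change and SD 16 to power a difference of that size, without connecting the two.

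The comparison of mean change is the first analysis listed under the primary outcome. If it shows no significant difference, a reader who trusts the 80% would take the result as fairly strong evidence against a 7-point benefit. The plan's own figures give the comparison less weight than that.

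**Working it through.** **Inputs.** Difference 7, SD 16, alpha 0.05, 75 per arm and 30% dropout (Section 9.2); two-tailed t-test and available cases (9.3.1); pilot SD 30, n=18 (4.2.1).

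**1. The plan's figure.** Normal approximation: power = Φ(difference/SE − 1.960), with SE = SD × √(2/n).

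- SE = 16 × √(2/75) = 2.613
- 7/2.613 = 2.679, and 2.679 − 1.960 = 0.719
- Φ(0.719) = 76.4%; the noncentral t gives 75.9%

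The stated 80% is not reproduced. The number needed per arm is 2 × (1.960 + 0.842)² × 16²/7², just over 82, so 83. A one-sided alpha of 0.05 would need 65 per arm, which matches neither 75 nor 58, and the planned test is two-tailed.

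**2. Evaluable sample size, SD 16.**

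| Per arm | Where it comes from | Normal | Noncentral t |
|---|---|---|---|
| 75 | all randomized | 76.4% | 75.9% |
| 58 | evaluable number for the responder endpoint | 65.4% | 64.7% |
| 56 | 25% missing (75 × 0.75 = 56.25) | 63.9% | 63.1% |
| 52.5 | 30% dropout (75 × 0.70) | 61.1% | 60.3% |

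**3. Detectable difference at 80% power, SD 16.** (1.960 + 0.842) × SE:

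- 75 per arm: 2.802 × 2.613 = 7.3 (7.4 by noncentral t)
- 52.5 per arm: SE = 16 × √(2/52.5) = 3.123, giving 8.7 to 8.8 (8.8 by noncentral t)

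**4. Link to the pilot SD.** The threshold argument is 30/√18 = 7.07. Assume that 30 is a score SD, equal at both visits. The SD of change is then 30 × √(2(1 − r)), where r is the baseline to 12-week correlation. Setting this to 16 gives r = 1 − 256/1800 = 0.858.

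That correlation recovers only the SD of 16, and hence 76% power. For 80% on the change score:

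- 75 per arm: SD at most about 15.3, so r = 1 − 15.3²/1800 = 0.87
- 52.5 per arm: SD at most about 12.8, so r = 1 − 12.8²/1800 = 0.91

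The pilot SD is imprecise. Its 95% interval under normality is about 22.5 to 45, so the r implied by SD 16 runs from about 0.75 to 0.94.

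**5. Range over r.** The documents give no correlation, so r is an assumption here. The table shows noncentral-t power for 7 points at 75 / 52.5 per arm; the normal approximation is higher by up to one point. The adjusted residual SD is 30 × √(1 − r²).

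| r | SD of change | Unadjusted | Adjusted residual SD | Adjusted |
|---|---|---|---|---|
| 0.5 | 30.0 | 29.5% / 22.0% | 26.0 | 37.4% / 27.7% |
| 0.7 | 23.2 | 44.9% / 33.3% | 21.4 | 51.1% / 38.2% |
| 0.8 | 19.0 | 61.2% / 46.5% | 18.0 | 65.8% / 50.6% |
| 0.9 | 13.4 | 88.8% / 75.4% | 13.1 | 90.3% / 77.6% |

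If 30 is itself the SD of change, the unadjusted entries in the first row apply and no correlation is involved.

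**The case against.** Enrolment was set by the responder proportion, which is how Section 4.2.1 measures the primary outcome; the mean-change sentence is a supporting claim. The shortfall with everyone analysed is only about 4 points. An SD of change below a score SD is normal, so 16 against 30 is not in itself a contradiction, and 18 pilot patients fix the SD only loosely. The 30% dropout has no stated time point, so fewer may be lost by week 12. Above 25% missing, the plan would impute rather than rely on available cases alone.

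Most of this stands, and it limits the point. It does not rescue the 80%. That figure fails with no dropout at all, gives 63% at the 25% missing that Section 9.3.1 treats as anticipated, and comes with no statement of how far imputation would restore power.

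Three stronger readings are tempting, and the documents do not support them:

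- A reader might infer that 80% power holds provided the correlation is near 0.86. That value gives only SD 16 and 76%. The unadjusted t-test needs about 0.87 with no dropout and 0.91 after it. Only a baseline-adjusted analysis with no dropout reaches 80% near 0.86.
- A reader might infer that 16 is wrong and 30 should replace it. The plan does not say what 30 measures, and at the lower limit of the pilot interval a correlation of 0.75 already yields 16. What is missing is a justification.
- A reader might infer that the comparison cannot detect 7 points. That depends on an unreported correlation: at r = 0.9 and 75 per arm, power is 89%.

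**Conclusion.** The concern holds in two parts of different strength.

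The firm part is arithmetic: with the plan's own difference, SD and alpha, power is 76% rather than 80% at 75 per arm, and about 60% at 52 to 53 per arm. This rests only on a two-sided t-test and, for the lower figure, on the 30% dropout applying by week 12 with nothing recovered by imputation.

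The second part is a missing justification: SD 16 is unsourced and about half the only DSI SD reported from data (16/30 = 0.53). Its effect on power cannot be fixed from the documents. Over correlations of 0.5 to 0.9, unadjusted power runs from about 30% to 89% at 75 per arm and from 22% to about 75% after dropout.

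Neither part touches the sizing of the responder endpoint or calls for a different enrolment target.

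**What to change.** In Section 9.2:

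- Restate the mean-change claim at the evaluable sample size. With SD 16 kept and 30% dropout applied, that is about 60% power for 7 points, or 80% power for about 8.8 points.
- Give the source of SD 16. If there is none, show a range derived from the pilot SD, with the correlation stated as an assumption, and say in Section 4.2.1 whether 30 is the SD of a score or of a change.
- State whether the figure refers to the unadjusted change score or the baseline-adjusted model, and take the numbers from the matching columns of the table above.

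The cost is one rewritten paragraph and a short recalculation, with no change in enrolment. The drawback is that the stated power for this comparison becomes less favourable.

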9.3 Feasibility

Approximately 325 individuals commence chronic HD in Winnipeg per year. At any time, there are approximately 700 prevalent patients receiving in-centre HD in Winnipeg. Assuming eligibility rate of 40% and a conservative 25% enrolment rate (based on previous studies and pilot data), the targeted sample size is achievable over the proposed 2-year recruitment period (see Section 4.1.1) and would amount to a maximum of 5 patients cycling per shift at each of the 4 HD units involved in the study at any one time. Based on our clinical cycling program experience (where we have up to 10 individuals cycling per shift), this rate of enrolment is easily achievable.

9.3 Description of Statistical Methods

9.3.1 Primary Outcome

Developed in consultation with a statistician ([name], Chronic Disease Innovation

Centre) familiar with RCTs and our study outcomes, analysis will be performed in an intention-to-treat manner on a case available basis. Change in DSI severity score from baseline to 12 weeks will be compared between groups by independent two-tailed t-test or Mann-Whitney U test depending on distribution and using generalized linear mixed models with study timepoint as a random effect and adjusted for baseline DSI score. In a subgroup of individuals whose baseline DSI score is >7, the proportion of individuals whose DSI severity score has improved by 7 or more points from baseline to 12 weeks will be compared between groups at each study time point using Chi-square test.

Multiple logistic regression will be performed to determine predictors of a >7 point change in DSI severity score over time and adjusted for time varying confounders using a marginal structural model. Interaction terms for sex and baseline DSI score will also be inputted into the model. Although study group will be the primary predictor in this model, other key predictors of symptom burden (including baseline DSI score, diabetes status, ischemic heart disease (IHD), age, gender, race, smoking status, serum albumin level, hemoglobin, baseline physical function, physical activity level and interaction terms for gender/intervention and baseline DSI score/intervention) will also be tested in a step-wise manner.

If **missing outcome data** is greater than anticipated (25%) we will impute them according to current FDA/NAS/NRC recommendations using multiple imputation with chained equations ⁸⁶⁻⁸⁸. Specifically, multiple imputation creates 20-40 complete datasets with plausible values from the model-based predictive distributions, and pooled estimates and standard errors are obtained through the use of Rubin's combining rules. These models are predicated on the assumption that the data are missing at random (MAR). Finally, the robustness of the inferences about treatment effects to violations of the MAR assumptions will be evaluated through a sensitivity analysis ⁸⁸.

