Study Endpoints Primary, Secondary and Mechanistic	Primary outcome: Change in symptom burden over time (12 weeks) as measured by Dialysis Symptom Index (DSI) severity score. Secondary outcomes: Change in generic health-related quality of life over time (12, 26, 52 weeks) as measured by EuroQol 5D-5L and EuroQol visual analogue scale Change in: modified symptom burden (modified DSI severity score); time for recovery post-HD; frailty status (Fried criteria); physical activity level (accelerometer and Godin-Shephard Leisure Time Physical Activity Questionnaire); exercise capacity (Incremental Shuttle Walk Test); self-

	efficacy for exercise (Self-Efficacy for Exercise Questionnaire; hospitalization rate (number hospital days admitted/patient year); all cause 1 year mortality
Brief Summary of Analysis	Sample size : The following assumptions were made: alpha 0.05; power 0.80; 30% dropout and 25% absolute difference in proportion of individuals in whom DSI severity score decreases by 7 points or more (minimal clinically important difference). Therefore, assuming a baseline symptom prevalence of 50% of individuals in each study group, 150 patients (75 in each arm) will be randomized and we will be able to detect a 25% reduction in the primary outcome.
	Primary analysis : Intention-to-treat, available-case basis, in the intervention versus control arm, using Chi-square test and logistic regression for categorical outcomes and t-tests/MannWhitney U for continuous outcomes.
	Secondary outcomes : Descriptive statistics, Kaplan Meier analysis, Poisson regression and linear mixed modeling and will be used as appropriate.

SCHEMATIC OF THE STUDY DESIGN

Enrolment and consent: Once informed consent is obtained, the Dialysis Symptom Index (DSI) will be administered to all participants. Those who score 0 on the DSI (no symptoms) will be deemed ineligible for the study

Randomization: To avoid bias, randomization will be performed following the baseline assessment.

Intervention phase: Participants in "intervention" group will receive study intervention during this time.

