9 STATISTICAL CONSIDERATIONS

9.1 Statistical and Analytic Plan

An outline of the analytic methods are given below.

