9.3.3 Secondary Outcomes and Analyses

We will repeat the primary outcome analyses that compared change in DSI from baseline to 12 weeks between groups, instead looking at change from baseline to 26 weeks and 52 weeks.

Change in EQVAS over time will be compared between study groups using Student's T-test. As well, we will compare the difference in proportion of individuals who develop new deficits (score of 2 or 3) in each domain of the EQ5D-5L over time. The degree to which change in symptom burden correlates with change in EQVAS will be assessed using Spearman and Pearson's correlation coefficients as indicated based on distribution of the data. Change in all other secondary outcomes over time will be compared between groups using the appropriate parametric and non-parametric statistical tests depending on data type and distribution. Bonferroni adjustments will be made for secondary outcomes to adjust for multiple study timepoints. Hospitalization will be analyzed using Poisson regression. For all analyses, two-sided p < 0.01 will be statistically significant. Statistical analysis will be performed using SAS 9.3 (Carey, NC).

We will validate the Godin Shepard Leisure-Time Exercise Questionnaire using accelerometry data. Correlation between Godin Questionnaire Score and active minutes (light, moderate and moderate-vigorous activity) measured by accelerometry at each study assessment time point will be assessed using Pearson or Spearman correlation depending on distribution of the data. Internal consistency of the Godin questionnaire will be assessed using Cronbach alpha and Intraclass Correlation Coefficient. In those individuals in which active minutes measured using accelerometry did not change between assessment periods (change of less than 10% from baseline), test re-test reliability of the Godin Questionnaire will be assessed using Kappa statistic. Responsiveness will be modelled using linear regression with Godin questionnaire score as the primary predictor of active minutes measured by accelerometry. Additional predictors including sex, age, diabetes and other comorbidities will be added to the model as sample size will allow.

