9.3.6 Final Study Analysis

The final study analysis will report the results of the above statistical analysis plan. Any additional analyses will be identified as ad hoc. A final clinical studies paper(s) will be prepared.

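### The mixed model for DSI change names timepoint as its only random effect and gives no participant term, so the clause should be replaced by one fully stated model (minor)

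*Combined protocol and SAP*

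**What the plan says.** Section 9.3.1 takes the change in DSI severity from baseline to 12 weeks and compares it between arms by t-test or Mann-Whitney, and also "using generalized linear mixed models with study timepoint as a random effect and adjusted for baseline DSI score". That clause is the whole specification. The only interactions named in the section, sex/gender and baseline DSI, belong to the logistic regression. The following sentence, on responders among participants with a baseline DSI above 7, says that proportions "will be compared between groups at each study time point using Chi-square test".

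Section 9.3.3 repeats the primary analyses, "instead looking at change from baseline to 26 weeks and 52 weeks".

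The model's standing differs between places. Section 9.3.1 sets it beside the t-test under the primary outcome without ranking the two. The synopsis describes the primary analysis as "using Chi-square test and logistic regression for categorical outcomes and t-tests/MannWhitney U for continuous outcomes", with no mixed model. For secondary outcomes it lists "Descriptive statistics, Kaplan Meier analysis, Poisson regression and linear mixed modeling and will be used as appropriate".

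Section 9.1 introduces all this with "An outline of the analytic methods are given below". Section 9.3.6 then states that "The final study analysis will report the results of the above statistical analysis plan" and that anything further is ad hoc.

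**The concern.** DSI is measured on the same people at baseline, 12, 26 and 52 weeks. In a model of repeated values, the random part has to carry the correlation between visits of one participant. A random effect for timepoint does something else: it lets the visits differ in overall level and leaves the values within a participant independent. Timepoint is also a design factor with three chosen post-baseline levels, which would normally be fixed.

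So the one structural rule that the plan states either has nothing to act on (one visit) or does not do the job required (several visits). Two analysts could follow the clause and fit different models. One of those models gives confidence intervals that are too narrow, around an average over the year. That average is not the 12-week effect if the effect changes with time. Section 7.4.3 lets both arms cycle after the intervention phase where a clinical program is offered, so a changing effect is plausible.

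**Working it through.** The plan gives no figure for this model, so there is none to reproduce. Its sample size of 58 per arm rests on responder proportions (50% against 25%, section 9.2) and does not involve the model.

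**Inputs**
- Participants per arm: 75 less 30% dropout = 75 × 0.70 = 52.5, taken as 52 (section 9.2).
- SD of change: 16, from "7-point difference in mean change in DSI severity score using standard deviation of 16" (section 9.2).
- Follow-up visits: 12, 26 and 52 weeks (section 7.2).
- Correlation r between DSI scores of one person at any two visits: not in the documents. Assumed equal for all pairs, at 0.3, 0.5 or 0.7.
- No true arm effect.

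**If only the 12-week change enters.** Each participant contributes one record and timepoint has one level. Its variance is not identifiable, but the arm estimate and its standard error are those of an ANCOVA. Simulated type I error at a nominal 5% (10,000 runs per r) is 4.7%, 5.1% and 5.1%.

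**If the three changes are stacked with one arm effect**
1. The change has variance 2σ²(1 − r) = 16². After adjustment for baseline, the residual variance is σ²(1 − r²), so the residual SD is 16 × √((1 + r)/2).
2. Two follow-up values of one person keep a residual covariance of σ²(r − r²), so the residual correlation is ρ = r/(1 + r).
3. The single-visit standard error is residual SD × √(2/52).
4. The stacked model treats the three values as independent and reports that figure divided by √3.
5. The true standard error is the reported one × √(1 + 2ρ).
6. The type I error is 2 × (1 − Φ(z/√(1 + 2ρ))), with z = 1.96 for 5% and 2.576 for 1%.

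| | r = 0.3 | r = 0.5 | r = 0.7 |
|---|---|---|---|
| Residual SD | 12.90 | 13.86 | 14.75 |
| Residual correlation ρ | 0.231 | 0.333 | 0.412 |
| Single-visit SE | 2.53 | 2.72 | 2.89 |
| Reported SE, stacked | 1.46 | 1.57 | 1.67 |
| True SE, stacked | 1.77 | 2.03 | 2.26 |
| Shortfall | 17% | 23% | 26% |
| Type I error at 5% | 10.5% | 12.9% | 14.7% |
| Type I error at 1% (threshold in section 9.3.3) | 3.3% | 4.6% | 5.6% |

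A simulation of the stacked fit (10,000 runs per r) gave 10.7%, 13.1% and 14.5% at 5%, in line with the formula.

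**Sensitivity.** If follow-up visits resemble each other more than they resemble baseline, so that ρ itself is 0.3, 0.5 or 0.7, the standard error is 21%, 29% or 35% too small and the type I error is 12%, 17% or 21%.

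**The model in fix (b).** Its 12-week contrast gave a simulated type I error of 4.3%, 5.1% and 5.0% (4,000 runs per r).

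**The case against.** The strongest reply is that the natural reading is harmless. The sentence takes 12-week change as its response, and section 9.3.3 repeats the analysis separately for the later visits. That leaves a redundant term in a sound baseline-adjusted comparison. This stands, and it is why the point is minor. It does not make the clause usable, because the one random effect it asks for could then not be fitted.

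The support for stacking is limited. The phrase about each study time point belongs to the Chi-square sentence, and the separate repeats in section 9.3.3 satisfy it. What remains is that naming timepoint as an effect presupposes more than one timepoint. That shows unclear wording, not an intention to treat one person's visits as independent.

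A reader might also infer that timepoint is meant as random within participant, and that this too inflates error. The documents do not support a separate harm claim. With one record per participant and visit, independent timepoint components cannot be told apart from the residual, so that version is the stacked model again. A version with a random slope but no participant intercept has no basis in the text. An unstructured covariance gave 5.8%, 5.2% and 5.5% for the averaged arm effect (4,000 runs per r), close to nominal.

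Finally, the model is probably supporting. Section 4.2.1 defines the primary outcome as a responder proportion, section 9.2 sizes the trial on it, and the synopsis leaves the mixed model out of the primary analysis. The reply that section 9 is only an outline is weaker, since section 9.3.6 treats it as the plan to be reported.

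**Conclusion.** The clause needs replacing; severity is minor. As written, its random effect cannot be estimated on the best-fitting reading, and on the stacked reading it gives anti-conservative inference about a one-year average. The inflation to 10.5–14.7% at a nominal 5% applies only to stacking. It rests on 52 per arm, an SD of change of 16, equal correlation between all visits, and assumed correlations of 0.3 to 0.7.

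A reader might infer that the trial's primary result carries an inflated false-positive rate, or that the plan commits to a wrong model. Neither follows. The text does not forbid a participant effect. The t-test, Mann-Whitney and Chi-square comparisons do not depend on this model, and neither does the sample size based on responders.

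**What to change.** Delete the words that make timepoint a random effect and state one of two models before the analysis.

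(a) An ANCOVA of 12-week DSI change on arm and baseline DSI, repeated at 26 and 52 weeks as section 9.3.3 already provides. This is closest to the present sentence.

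(b) A linear mixed model for DSI change at the three follow-up visits, with fixed arm, categorical timepoint, arm-by-timepoint and baseline DSI, and an unstructured within-participant covariance. Report the 12-week arm contrast as the model's main estimate. Let its 26- and 52-week contrasts replace the separate mixed-model repeats in section 9.3.3, so that the same comparisons are not made twice.

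In either case, label the model as primary or supporting, so that the synopsis and section 9.3.1 agree.

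The cost is a change of wording only: no new data, visits or participants, and the same software.

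### Section 9.3.1 does not match the 12-week responder outcome that 4.2.1 defines and 9.2 sizes, names no deciding test, and is left with two conflicting significance levels

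*Combined protocol and SAP*

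**What the plan says.** Section 4.2.1 introduces the primary outcome as change in DSI severity score to 12 weeks and then makes it a responder outcome: "This will be measured as the proportion of individuals who have a decline of 7 points or more in symptom burden". No baseline score is required beyond the entry condition in section 4.1, a DSI above 0. Section 9.2 sizes the trial on the same proportion, 50% v 25%: "A sample size of 58 patients in each arm will allow us to detect this difference with 80% power (alpha 0.05"). It also claims that the sample can "detect a 7-point difference in mean change in DSI severity score using standard deviation of 16 with 80% power and alpha 0.05".

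Section 9.3.1, the primary analysis section, contains the following, in this order:

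- Mean change to 12 weeks, tested by t-test or Mann-Whitney according to how the data are distributed, together with a generalized linear mixed model adjusted for baseline DSI.
- A responder comparison limited to part of the sample: "In a subgroup of individuals whose baseline DSI score is >7, the proportion of individuals whose DSI severity score has improved". Improvement here means a fall of at least 7 points. The sentence gives the 12-week interval, yet says that the proportion "will be compared between groups at each study time point using Chi-square test".
- A multiple logistic regression for "predictors of a >7 point change in DSI severity score over time", with stepwise covariates and a marginal structural model.

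The synopsis assigns chi-square and logistic regression to categorical outcomes, and t-tests or Mann-Whitney to continuous ones, without ranking them. Section 9.3.1 gives no significance level. The synopsis and section 9.2 use 0.05; section 9.3.3 says "For all analyses, two-sided p < 0.01 will be statistically significant". On timing, section 3 puts 12, 26 and 52 weeks in the primary objective and hypothesis. The synopsis objectives and section 4.2.1 make 12 weeks primary, and section 4.2.3 lists 26 and 52 weeks as secondary.

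**The concern.** The analysis section should contain the comparison that was defined and sized, and should say that it decides the trial. Here the responder test appears only in a restricted form, after a mean-change test, and neither is marked as primary. A reader of the final report could not tell from the plan which p-value was meant to count, or against which threshold. If the choice can be made after the data are seen, the stated error rate no longer holds.

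The baseline restriction also changes the question. Patients who start at 1 to 6 cannot fall by 7, so leaving them out alters the population and the size of effect being estimated. Read literally, the cut-off also drops patients who start at exactly 7, who can respond.

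**Working it through.** **Inputs.** From section 9.2: 50% v 25% responders; 58 evaluable and 75 randomised per arm; 30% dropout; alpha 0.05; 80% power; a 7-point mean difference with SD 16. From section 9.3.3: two-sided p < 0.01. Evaluable after dropout: 75 × 0.70 = 52.5, taken as 52.

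**1. Reproduce the plan's figure.** Two proportions, pooled variance under the null, mean proportion 0.375:

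n = [z(α/2)·√(2 × 0.375 × 0.625) + z(power)·√(0.50 × 0.50 + 0.25 × 0.75)]² / 0.25²

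At 0.05: (1.960 × 0.6847 + 0.8416 × 0.6614)² / 0.0625 = 57.7, so 58 per arm, with 80.2% power. Section 9.2 therefore sizes an uncorrected two-sided 5% comparison of two proportions with no baseline restriction.

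**2. The same design at 0.01.** Power at 58 per arm = Φ[(0.25 × √58 − 2.576 × 0.6847) / 0.6614] = Φ(0.21) = 58.4%. For 80% power: (2.576 × 0.6847 + 0.8416 × 0.6614)² / 0.0625 = 86.1, so 87 evaluable per arm.

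**3. Two candidate tests at 0.05.** This was simulated with 60,000 trials of 52 per arm. Assumptions: normal change rounded to whole points, SD 16, 25% control responders. A share of 0, 5 or 10% start too low to fall by 7; the documents do not give this share. A 50% v 25% contrast corresponds to a shift of 0.6745 × 16 = 10.8 points before low-baseline patients are capped. Ranges run over the three shares.

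| True shift | t-test significant | Restricted responder test significant | Exactly one of the two significant |
|---|---|---|---|
| 10.8 points | 91.7–92.5% | 71.6–77.3% | 17.2–22.2% |
| 7 points | 58.9–59.9% | 36.6–40.7% | 27.0–29.4% |

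With no effect, each test alone rejects in about 5% of trials. At least one rejects in 8.2–8.4% at 0.05, and in 1.6–1.7% at 0.01.

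**4. What the baseline restriction contributes.** Against the unrestricted responder test, the t-test disagrees about as often: 17.2–24.2% and 27.0–30.1%. The restricted and unrestricted responder tests differ from each other in only 4.6–7.0% of trials at 5–10% low baseline. The disagreement in step 3 therefore comes from mean change versus responder.

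The estimand does move. If 50% v 25% holds overall, the restricted difference is 25/0.95 = 26.3 or 25/0.90 = 27.8 points. If it holds only within the restricted set, the overall difference is 25 × 0.95 = 23.8 or 25 × 0.90 = 22.5 points. Power can rise or fall accordingly. At 52 per arm the restricted test has 77.1–78.8% in the first case and 71.1–73.5% in the second, against 75.7% for an unrestricted 50% v 25%.

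**The case against.** A reader might infer that the sized analysis is found nowhere in the plan. That goes too far. The synopsis lists chi-square and logistic regression for categorical outcomes under its primary analysis, with no baseline limit, and the logistic model in 9.3.1 is not confined to the subgroup and has study group as its main predictor. This stands as a limit on the point, but does not remove it. The synopsis sorts tests by data type without choosing one. The logistic model uses a change above 7 rather than 7 or more, runs over time and selects covariates stepwise, so it is a different analysis.

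It is also tempting to say that the plan defines the outcome in everyone randomised. The documents say intention-to-treat on available cases; what they support is that 4.2.1 and 9.2 set no baseline restriction.

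The visit is largely settled. Besides the synopsis, 4.2.1, 4.2.3 and 9.2, section 9.3.3 describes 26 and 52 weeks as repeats of the 12-week primary analyses and applies Bonferroni adjustment across visits for secondary outcomes. Section 3 and the stray wording in 9.3.1 are out of line with these. They do not justify treating all three visits as equal primary tests, with the larger error rate that would imply.

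The p < 0.01 sentence sits under secondary outcomes, soon after the Bonferroni sentence, and may have been meant only for them. That is plausible, but the sentence covers all analyses and 9.3.1 gives no level to override it.

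Finally, much of the disagreement is the ordinary cost of dichotomising. With no low-baseline patients, a separate run found the t-test alone significant in 16.5% of trials and the responder test alone in 1.1% (10.8-point shift), and 23.8% v 3.9% (7-point shift). That explains the pattern, but the plan still does not say which test decides.

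**Conclusion.** The point holds. As written, section 9.3.1 does not carry the outcome defined in 4.2.1 and sized in 9.2, and neither the deciding test nor its level is fixed. The two harms are alternatives and should not be added together:

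- If 0.01 governs, power at 58 per arm is 58.4% rather than 80%, but either-test error is only 1.6–1.7%.
- If 0.05 governs, the planned power at 58 per arm stands, but either-test error is about 8% and the two tests disagree on significance in roughly 17–29% of trials.

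The power figures follow from the plan's own inputs. The error and disagreement figures rest on assumed normal change, SD 16, 52 per arm and 0–10% low baseline. A reader might also take the baseline restriction for a source of bias or the main cause of disagreement. Neither is supported: it selects on a pre-randomisation score, so the randomised comparison is preserved, and it changes the significance result in only about 5–7% of trials (assumed 5–10% low baseline). What it changes is the estimand.

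**What to change.** In section 9.3.1, name one primary analysis: the chi-square comparison, by randomised group, of the proportion with a DSI fall of 7 or more from baseline to 12 weeks. It should follow the plan's intention-to-treat and missing-data rules and carry no baseline restriction, at two-sided alpha 0.05 as used in 9.2. Patients below 7 at baseline who have outcome data count as non-responders.

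State in 9.3.3 that p < 0.01 applies to secondary outcomes only, or else restate the power in 9.2 as 58.4% at 58 per arm. Limit the primary objective in section 3 and the primary comparison in 9.3.1 to 12 weeks. Label mean change, the mixed model, the logistic model and the restricted responder analysis as supportive, and write the threshold as 7 or more throughout.

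The cost is a wording amendment with ethics review under section 10.2, and no new data. There is a statistical price: under a 7-point shift at 52 per arm, with no low-baseline patients, the responder test has about 41% power against 60% for mean change. It is nevertheless the endpoint that the trial defined and sized, and the amendment should state this trade-off.
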